Recruitment, eligibility, and informed consent/assent. We will recruit N=60 male adolescents (30 in each of 2 arms) to test *Safe South Africa* in a pilot RCT to generate data for a future fully-powered RCT. This pilot RCT consists of a behavioral group-based intervention (10-20 adolescents per group) delivered by a facilitator in 2-hour sessions, once a week for a total of two weeks after school, on school premises with take home activities to deepen behavioral practice and engagement. We implement recruitment, consent and assent procedures, and eligibility criteria same as Aim 1 (see above). Consent and assent procedures will occur twice during Aim 3. First, consent and assent will occur at the first point of contact, after screening for eligibility and prior to gathering baseline assessment. We seek consent and assent prior to gathering baseline assessment because this data will provide valuable feasibility and acceptability data on who is eligible for the community based intervention but who choose not to proceed to enrollment. Second, consent and assent will be sought at the enrollment session which includes a behavioral run-in an intensive methodological approach for discussing pros and cons of trial participation, detailed at the NIH Randomized Behavioral Clinical Trials Institute (attended by M-PI [name]).¹⁵⁹ This method focuses on thoroughly discussing ethical considerations prior to randomization (and in doing, also optimizing recruitment and retention in the trial). This procedure involves a discussion of pros and cons in the order shown in Figure 1 as part of study orientation, prior to randomization.

Figure 1: Study orientation and ethical discussion		
	Enrolling in the study	NOT enrolling in the study
Pros of participation	3 – Discuss third pros of enrolling in the study	2 – Discuss second pros of not enrolling in the study
Cons of participation	4 – Discuss last cons of enrolling in the study	1 – Discuss first cons of not enrolling in the study

The idea of this behavioral run-in is to provide a more in-depth orientation session after participants have been

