
Reimbursement. Adolescents will receive 50 Rand (consisting of 25 Rand to offset time and 25 Rand to offset travel costs) for the baseline outcome assessment, 60 Rand (consisting of 35 Rand to offset time and 25

Rand to offset travel costs) for the 1-month outcome assessment, and 70 Rand (consisting of 45 Rand to offset time and 25 Rand to offset travel costs) for the 6-month outcome assessment. In addition, adolescents will receive 50 Rand (consisting of 25 Rand to offset time and 25 Rand to offset travel costs) for the enrollment session and filling out the satisfaction assessments that occur after the first session. Adolescents in the intervention arm only, will receive 60 Rand (consisting of 35 Rand for time and 25 Rand for travel) for satisfaction assessments filled out after the second session.).

Sample Size and Power Considerations. The primary objective of this pilot is to test feasibility, acceptability, and generate meaningful effect size estimates for a future fully-powered RCT. A fully-powered study is not our aim. We believe 60 adolescents (30 adolescents per arm) is adequate to examine feasibility and acceptability. We increase sample size by 10% as a conservative estimate during baseline recruitment to 66 adolescents to account for loss to attrition; our previous HIV intervention trial with similar aged adolescents in similar settings had 100% retention at the last follow-up timepoint.^{45,192} We considered sample size needed based on the goals of increased condom use at last sex by a third or double as shown in other adolescent HIV behavioral trials,^{20,193,194} and reduced sexual assault by half as shown in our previous trials of the *SAFE* intervention. To examine moderate effects (e.g., 0.50) we would need 200 adolescents, or 100 adolescents per arm, beyond the scope of this pilot. Thus, we focus on rigorously testing acceptability and feasibility.

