Analysis. For acceptability, we conduct the same analysis as described for Aim 2, setting 80% reporting positive ratings as a marker of acceptability and examining process data on satisfaction with clarity, structure, content, delivery, location, and timing of the intervention. For feasibility, we evaluate fidelity, setting 80% fidelity as a marker of acceptability. We also evaluate feasibility in regards to attendance rates, treatment retention rate, retention during outcome timepoints, and balance during randomization. For these data, individual ANOVA will be conducted to compare groups (*SAFE South Africa* vs. Control) on the continuous variables of number of sessions attended. For treatment retention rate (dichotomous), a chi-square analysis will be used. For success of random assignment in equating groups, we compare groups on demographic characteristics and primary risk factors for HIV and IPV. If groups differ on any variables that show a relation to outcomes, outcome analyses will be conducted both with and without adjusting for these covariates. For trial outcomes, preliminary analyses will include studies of patterns of missing data, dropout rates, and correlations effect size estimates with small samples have large standard errors so we use pilot data to assess hypothesized intervention effects.¹⁹⁵ We will examine key variables for skewness, variability, missing data, and outliers, with transformations to achieve normality if needed. We will examine descriptive statistics for main outcomes and mediators with extreme scores or deviations from normality to be addressed in subsequent analyses. Baseline differences between groups on demographic variables will be examined using *t*-tests and variables that show differences will be included as covariates in outcome analyses. Generalized estimating equations (GEE) will be used to compare intervention and control group on the main study outcomes following intention-to-treat principles. In exploratory analysis, we look at directions of hypothesized effects for our outcomes. While we are underpowered to test mediation effects directly, we will explore differences between study arms in hypothesized mediating and moderating variables. We will obtain the between treatment condition effect size estimates (with 95% confidence intervals) at each assessment (e.g., Cohen's *d* or *h*) to help determine necessary sample size for future fully-powered RCT.¹⁹⁶

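### The plan makes no provision for clustering by delivery group in the intervention arm, so the effect-size intervals meant to inform the next trial are too narrow at any positive within-group correlation

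*Combined protocol and SAP*

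**What the plan says.** Under Specific Aim 3, the recruitment paragraph states "We will recruit N=60 male adolescents (30 in each of 2 arms" and describes "a behavioral group-based intervention (10-20 adolescents per group) delivered by a facilitator". It does not give the number of groups. The Goals paragraph describes the control condition as a packet of existing brochures and helpline details, so controls form no delivery groups.

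The Analysis paragraph states: "Generalized estimating equations (GEE) will be used to compare intervention and control group on the main study outcomes following intention-to-treat principles". It names no cluster unit, working correlation, or group, facilitator or school term. It continues: "We will obtain the between treatment condition effect size estimates (with 95% confidence intervals) at each assessment", and gives the purpose as "to help determine necessary sample size for future fully-powered RCT".

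Sample Size and Power Considerations counts effect-size estimates for the later trial among the pilot's primary objectives. It also says "A fully-powered study is not our aim". Neither that paragraph nor Analysis mentions an ICC or a design effect.

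Randomization & Retention describes permuted-block randomisation of adolescents but places the control arm at another school.

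**The concern.** Boys in the same group share a facilitator, a discussion and a set of peers, so their later answers are likely to be correlated. Here that correlation is part of the intended mechanism. Section C (conceptual model and core components) relies on peer reinforcement, debate that corrects perceived norms, and a group exercise that shows boys what the others think. An ICC of exactly zero would be hard to square with that theory.

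Because only the intervention arm is grouped, the design is partially nested: the variance of one arm's mean is inflated and the other's is not. A GEE clustered on the boy accounts for repeated measures within a boy but not for correlation between boys in one group. An ordinary interval for d or h accounts for neither.

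At stake is the stated precision of the effect sizes, which the plan treats as an input to the design of the full trial.

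**Working it through.** **Inputs from the documents.** 30 boys per arm; groups of 10-20; d or h with 95% intervals; 0.50 as a moderate effect. **Assumed, because the documents give no value:** ICC 0.01, 0.05 and 0.10; control arm unclustered.

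**1. Number of groups.** 30/20 = 1.5 and 30/10 = 3, so two or three. With the 10% recruitment allowance (60 × 1.10 = 66, or 33 per arm), 33/20 = 1.65 and 33/10 = 3.3, so again two or three.

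**2. The plan's own larger sample size.** The plan says "To examine moderate effects (e.g., 0.50) we would need 200 adolescents, or 100 adolescents per arm". Alpha and power are not stated, so this cannot be reproduced. At d = 0.50 and two-sided 0.05, independent observations need 63, 85 and 104 per arm for 80%, 90% and 95% power; 100 per arm gives 94.2%. Whether the figure contains any allowance for clustering cannot be determined.

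**3. Ordinary interval.** At d or h = 0, SE = sqrt(2/30) = 0.258, so the 95% half-width is 1.96 × 0.258 = 0.506.

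**4. Partially nested correction.** DEFF = 1 + (m − 1) × ICC in the intervention arm and 1 in the control arm. With equal arms, the SE ratio is sqrt((DEFF + 1)/2). For uneven groups, m is Σm²/Σm; for 20+10 that is (400 + 100)/30 = 16.67.

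| Groups | ICC | DEFF | SE ratio | Half-width (0.506 × ratio) |
|---|---|---|---|---|
| 3 of 10 | 0.01 | 1.09 | 1.022 | 0.517 |
| 3 of 10 | 0.05 | 1.45 | 1.107 | 0.560 |
| 3 of 10 | 0.10 | 1.90 | 1.204 | 0.609 |
| 2 of 15 | 0.01 | 1.14 | 1.034 | 0.523 |
| 2 of 15 | 0.05 | 1.70 | 1.162 | 0.588 |
| 2 of 15 | 0.10 | 2.40 | 1.304 | 0.660 |
| 20+10 | 0.01 | 1.16 | 1.038 | 0.525 |
| 20+10 | 0.05 | 1.78 | 1.180 | 0.597 |
| 20+10 | 0.10 | 2.57 | 1.335 | 0.676 |

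**5. Coverage of the unadjusted 95% interval**, 2Φ(1.96/ratio) − 1. For three groups of 10 / two of 15 this is 94.5% / 94.2% at ICC 0.01, 92.3% / 90.8% at 0.05 and 89.6% / 86.7% at 0.10. A simulation of 40,000 runs per setting gave 94.3% / 94.2%, 92.6% / 90.5% and 89.4% / 86.3%. With ICC 0 it gave 95.0% / 94.7%.

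**6. What the widening still leaves out.** It keeps the normal multiplier of 1.96. With Satterthwaite degrees of freedom based on group means at ICC 0.05, three groups of 10 give about 5.5 degrees of freedom and a half-width of 0.71; two of 15 give about 2.5 and 1.07.

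**7. Consequence for a later trial** at d = 0.50, 80% power, two-sided 0.05 and groups of 15 in one arm only. Per arm, n = (1.96 + 0.84)²/0.25 × (DEFF + 1), where the first factor is about 31.4. DEFF = 1 gives 63; ICC 0.01, 0.05 and 0.10 give 68, 85 and 107.

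**The case against.** The strongest reply is that this is a feasibility pilot. Section B calls the outcome hypotheses an exploratory secondary aim, and Analysis looks at directions of effect and warns that small-sample effect sizes have large standard errors. No decision rule attaches to a p-value. Clustering does not bias d or h, and a half-width near 0.5 is too wide to size a trial on its own. All of that stands and limits the weight of the point. It does not remove it: the warning concerns sample size, not clustering, and the intervals are a named deliverable for planning.

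Several stronger readings are tempting but not supported:

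- **That the plan declares the boys independent.** It is silent. Independence between boys is what the ordinary methods assume.
- **That intervals could be 40% too narrow.** That needs every group to hold 20 boys, which 30 boys cannot fill. The 20+10 split gives about 34% at ICC 0.10.
- **That all excess false positives in a simulated GEE come from clustering.** At 30 per arm such a model rejected about 6% of the time with ICC 0, from small-sample bias in the sandwich variance. Only the rise above that is due to clustering.
- **That one ICC, such as 0.05, should be carried forward.** No document supports one value over another, and at 0.01 the effect is only 2-4%.
- **That the next trial will repeat the omission.** Its design is not in these documents.

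A further objection is that the formula treats controls as unclustered. That is fair. If the arms really come from different schools, one per arm, school is confounded with arm and no variance correction removes it.

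**Conclusion.** The point holds as an omission: delivery-group clustering is not provided for, and an interval that ignores it is too narrow at any positive ICC. Over an assumed ICC of 0.01 to 0.10 the shortfall in the standard error runs from about 2% to 34%, depending on how the 30 boys are grouped. For equal-sized groups, true coverage of a nominal 95% interval falls from about 94% to 87-90% across that range. The direction follows from the design and the programme's peer mechanism; the size rests on the assumed ICC.

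The point should be addressed, but it does not threaten the feasibility and acceptability aims. It arises even if boys are randomised individually within one school. The correction shown here is valid only if the control arm can be treated as unclustered, which the text on the control school leaves open.

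**What to change.** 1. Reconcile the control arm's separate school with individual permuted-block randomisation before settling the variance method. If there is one school per arm, state that school and arm are confounded and do not present a widened interval as having corrected this.
2. Record delivery-group and facilitator identifiers for each intervention boy from the first session.
3. In Analysis, name the GEE cluster unit. Beside each unadjusted d or h interval, report intervals widened by sqrt((DEFF + 1)/2) at ICC 0.01, 0.05 and 0.10, using the actual group sizes and mandating no single value.
4. State that two or three groups cannot support an ICC estimate or a reliable group-level robust variance, so simply clustering the GEE on group is not a remedy, and that the widened intervals still omit the degrees-of-freedom penalty.
5. Apply a design effect, with its assumed ICC stated, when sizing the full trial.

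The cost is two recorded identifiers, a few sentences and one extra table. Reported intervals become about 2-34% wider. Recruitment and delivery do not change under items 2 to 5; item 1 may require a design clarification.

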Survey of Social Ecology. In preparation for later stages of Aim 2 and for Aim 3, we begin by conducting a school-wide survey to better understand the social ecology of the school community with N=100 male and female adolescents. This survey comprises Part 1 (preparations for the *Safe South Africa Intervention*), by providing a data-driven evaluation of risk and protective factors for HIV and IPV. The results of the survey of social ecology will help to generate evidence-driven social norms messaging used as content for the intervention being tested in Part 2, the stage corresponding to actual roll-out of the male adolescent behavioral intervention (the open pilot test of the intervention and the randomized pilot trial of the intervention). For the survey, we will recruit a convenience sample of both male and female adolescents attending our chosen intervention school by visiting classrooms, briefly explaining the purpose of the anonymous survey.

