Recruitment for Survey. This survey will guide the development of intervention content that is specifically tailored to the adolescents that are the population being targeted in this intervention. The survey generates specific age and contextual data that will be integrated into a final intervention model that is adapted for the South African population and setting where the intervention is being tested. We will recruit a convenience sample of both male and female adolescents attending our chosen intervention school site by visiting classrooms, briefly explaining the purpose of the anonymous survey. Inclusion criteria include: (1) adolescents attending the high school will be included regardless of gender and age. Interested adolescents go through assent procedures if they are under 18 years of age. Adolescents are excluded if parents fail to provide consent or adolescents do not provide informed assent. We anticipate the age to be 13-18 years but school-going ages vary widely in South Africa due to delayed start of school and pass/fail criteria that may hold back students based on performance. We focus on all adolescents in the school environment. Although the target of the *Safe South Africa* intervention itself focuses on male adolescents 15-17 years of age (for the open pilot in the second half of Aim 2, and the randomized pilot trial in Aim 3), we feel that expanding our survey of social ecology to include all students regardless of age in the high school environment is warranted. We specifically chose to include adolescents who are both younger and older than our target intervention age group in this survey of the social ecology to provide a more complete picture of norms in the school community. This information on how norms develop and are shaped in the ages leading up to, and immediately after, our actual intervention target population age range of 15-17 years, is relevant to the developmental-tailoring of intervention content. We also purposively include females as well as males in this school ecology survey even though the intervention itself targets males. This is because norms around HIV risk behavior, IPV, and gender are not shaped only by male adolescents (who are the target of our gender-specific intervention). Females also shape the social ecology relating to HIV and IPV behaviors among males. As such, we feel that including females in the survey of social ecology will provide more detailed information on how both female and male perspectives shape the social environment including roles, norms, and expectations relating to male-specific HIV risk behavior and IPV perpetration. Thus, we feel that eliciting female, as well as male perspectives, in the social ecology survey during Aim 2 enriches the scientific data that we generate to refine the intervention that will be piloted in Aim 3.

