Design. This is a randomized controlled trial where participants are prospectively assigned to two arms (Safe South Africa) versus the control of ordinary usual care. This will be a single blind study. Intervention participants will not be blinded to the condition they are in (the intervention group will receive the intervention first, with the control group given standard usual care. Study staff (e.g. intervention team) will not be blinded to the condition. Study staff (e.g., outcome assessment team) who assess outcomes after the experimental intervention has been delivered will be blinded to the condition participants have been assigned to. Blinding will be broken for data analysis. To reduce the risk of contamination, or that blinding will be broken by participants communicating to each other, we will request that participants in the intervention keep all activities and discussions to themselves. We will also assess whether blinding was successful by checking for contamination at the outcome assessments at 1- and 6-months. There is no chance that participants in the control group would participate mistakenly in the intervention so we assess for contamination in terms of sharing of intervention materials between the intervention and control group. Participants assigned to the control group will be screened for contamination. We will adjust for any contamination effects in analyses. Although this is a feasibility and acceptability trial, thus not designed to be fully powered to measure effects, we set out to create a study design that carefully adheres to elements outlined in the Consolidated Standards of Reporting Trials (CONSORT) Statement.¹⁵⁸ This pilot study adheres to a single blind, randomized pilot trial design with the end goal of informing a future fully powered RCT corresponding to a Phase III clinical trial.

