given time to consider the study in depth (following an initial consent and assent at baseline). In this behavioral run-in, we provide a thorough discussion of ethical considerations to complement traditional consent/assent procedures. This discussion focuses upon eliciting potential participants' perspectives of pros and cons of their potential trial enrollment to help them consider risks and benefits thoroughly, to explicitly acknowledge study challenges, and to engage in a meaningful interactive dialogue to overcome any misunderstandings of the study (including confusion on trial design and objectives, prevention misconception, and other ethical challenges documented by studies on related topics in similar settings).^{160,161} The approach avoids a "hard sell" or "pro-change" positions, but instead, focuses on enriching the informed consent and assent process to ensure meaningful informed and voluntary consent and assent.

Randomization & Retention. We will randomize adolescents in this 2-arm trial to an intervention arm (testing our *Safe South Africa* intervention, n=30) or a control arm (n=30) from a different school consisting of ordinary usual care (information on existing community resources for HIV and IPV). We considered comparing to a more stringent control, such as an existing rigorously empirical preventative interventions targeting prevention of HIV-IPV perpetration but this does not exist for adolescents in South Africa. We will randomize based on permuted blocked randomization chosen off careful consideration of randomization possibilities and training received at the NIH Randomized Behavioral Clinical Trials Institute. Permuted blocks will be based off of varying block lengths. This process will be repeated until target baseline enrollment is achieved. To retain participants, one data enterer will devote 50% time to tracking including: 1) at baseline, documenting multiple participant contact details and three individuals who know how to contact the family; 2) monthly contact via telephone or text; 3) follow up at least five times using different days, times, and methods. These strategies were successful in maintaining 100% attrition in [name] recent acceptability and feasibility trial with adolescents of similar age and similar South African communities.

Assessments. All measures utilized in the current study are well established, with adequate reliability and validity and tested in our prior studies. See **Table 2.**

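### The Aim 3 allocation rule cannot be carried out: boys are randomised individually by permuted blocks, yet the control arm comes from a different school

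*Combined protocol and SAP*

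**What the plan says.** All references are to section E, Methods, of the combined protocol and SAP.

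- **Aim 3, Randomization & Retention.** One sentence contains both rules. It opens "We will randomize adolescents in this 2-arm trial to an intervention arm" and goes on "or a control arm (n=30) from a different school consisting of ordinary usual care". On the mechanism: "Permuted blocks will be based off of varying block lengths. This process will be repeated until target baseline enrollment is achieved".
- **Aim 3, Design.** This is a trial "where participants are prospectively assigned to two arms". Contamination is handled by asking intervention boys to keep the content to themselves and by screening controls. Separation by school is not mentioned.
- **Aim 3, Recruitment, eligibility, and informed consent/assent.** Screening, baseline assessment, the enrolment session and second consent come first. The discussion of pros and cons takes place "as part of study orientation, prior to randomization".
- **Aim 3, Analysis.** The arms are compared at baseline to check the randomisation, outcomes are compared by GEE, and effect sizes with 95% confidence intervals are estimated at each assessment. No school term, stratum or cluster adjustment is given.
- **Aim 3, Sample Size and Power Considerations.** The primary objective is to "test feasibility, acceptability, and generate meaningful effect size estimates for a future fully-powered RCT".
- **Aim 2, Survey of Social Ecology and Recruitment for Survey.** Survey pupils are those "attending our chosen intervention school by visiting classrooms", and again "attending our chosen intervention school site by visiting classrooms". This survey supplies intervention content for Aim 3 as well.

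**The concern.** The two rules name different units of allocation, and staff cannot follow both. If the school wording is followed, the block sequence has nothing to decide. If the block sequence is followed, the school wording is false.

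The stakes depend on how many schools there are. With one school in each arm, every between-arm contrast is also a contrast between two schools. That affects the comparisons for the three exploratory hypotheses, the feasibility measure of balance after randomisation, and the effect sizes intended to help size the future trial. School is not a neutral label here: the conceptual model in section C treats the school's peers as the community whose norms drive behaviour, so the plan's own theory expects schools to differ on these outcomes.

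**Working it through.** **1. Can both rules hold?** By the time of randomisation a boy has been screened, assessed at baseline and seen at an enrolment session, so his school is already known. Suppose 60 boys, 30 from each of two schools, are individually allocated 30:30 without stratification. The chance that every control comes from one named school is 1/C(60,30), about 8 × 10⁻¹⁸. With blocks run within school it is zero. Individual randomisation therefore cannot produce the control arm described.

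**2. Does another section settle it?** Design refers to participants. Recruitment puts an individual orientation before randomisation. Analysis has no school component. No section says that schools are randomised or how many take part in Aim 3.

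**3. What if there is one school per arm?** Between-school degrees of freedom are 2(k − 1) for k schools per arm: 0, 2 and 4 for k = 1, 2 and 3. With two schools there are only two possible assignments, so the smallest two-sided randomisation p-value is 2/2 = 1.

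The plan has no figure of its own to reproduce on this point; 30 per arm is a feasibility choice. To show the scale I used:

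- m = 30 boys per school (Recruitment), and m = 100, the per-arm size that the sample-size section gives for an effect of 0.50;
- school ICC: not in the documents, assumed 0.01 to 0.10;
- an unadjusted comparison, not the planned GEE.

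Formulas:

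- design effect DE = 1 + (m − 1) × ICC
- type I error = 2 × [1 − Φ(1.96/√DE)]
- nominal half-width for d = 1.96 × √(2/m)
- half-width if the ICC were known = nominal × √DE

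| m | ICC | DE | Type I error | Half-width (nominal) |
|---|---|---|---|---|
| 30 | 0.01 | 1.29 | 8.4% | 0.575 (0.506) |
| 30 | 0.02 | 1.58 | 11.9% | 0.636 (0.506) |
| 30 | 0.05 | 2.45 | 21.0% | 0.792 (0.506) |
| 30 | 0.10 | 3.90 | 32.1% | 0.999 (0.506) |
| 100 | 0.01 | 1.99 | 16.5% | 0.391 (0.277) |
| 100 | 0.02 | 2.98 | 25.6% | 0.478 (0.277) |
| 100 | 0.05 | 5.95 | 42.2% | 0.676 (0.277) |
| 100 | 0.10 | 10.90 | 55.3% | 0.915 (0.277) |

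A t-test uses the within-school standard deviation. Replacing 1.96/√DE by 1.96 × √((1 − ICC)/DE) gives slightly higher type I error: 8.6% to 34.6% at m = 30 and 16.7% to 57.3% at m = 100. A simulated t-test (40,000 runs per cell) gave 8.5% to 34.3% and 16.6% to 57.6%. The tabulated error rates are therefore a little low.

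As m grows without limit, the half-width tends to 1.96 × √(2 × ICC), which is 0.277, 0.392, 0.620 and 0.877 for the four ICC values. More pupils do not remove the problem. Nor can this design estimate the ICC that the wider intervals would need.

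**The case against.** The strongest reply is that one school per arm is an inference. The singular wording comes partly from the Aim 2 survey, while the Language and Site Selection paragraphs speak of study sites and schools in the plural. Planning for boys talking to each other and sharing materials, randomising after an individual orientation, and checking the random assignment all fit arms that share schools. On that reading the different-school phrase is a stray, and none of the figures above applies.

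This is a fair reason to keep the figures conditional. It does not remove the contradiction: the plurals are compatible with two schools, and a stray phrase that fixes the source of the control arm still has to come out.

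A second reply is that this is a pilot which says it is not fully powered and looks at directions of effect, so type I error matters little. That stands for the tests. It does not answer the point about effect sizes, which are named in the primary objective and feed the next trial. The figures at 100 per arm describe a study the plan calls out of scope; they show only that enlarging the arms is no remedy.

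Third, individual randomisation would still leave clustering by delivery group (10 to 20 boys per group). That is correct, and the fix allows for it.

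**Conclusion.** The concern holds. The allocation rule is wrong as written, and this conclusion needs no assumption about the number of schools or the ICC. The confounding is conditional on one school per arm, which the sponsor must confirm. If that is the design, arm and school coincide with no between-school degrees of freedom, and neither GEE nor covariate adjustment can separate them.

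The numerical range rests on the assumed ICC and the unadjusted test. It shows scale and does not predict this trial's error rate. Because the rule cannot be executed and it feeds a primary objective, it should be corrected before Aim 3 enrols.

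**What to change.** State the unit of allocation and the number of schools, and make the Design, Randomization & Retention and Analysis paragraphs agree. There are three coherent routes.

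- **(a) One school per arm.** Describe allocation as by school and say how the schools were assigned. Delete the individual permuted-block text. Keep the baseline comparison but label it a comparison of schools. Report outcomes by arm descriptively, and do not use between-arm tests, intervals or effect sizes as evidence for the hypotheses or as inputs to the next trial's sample size. *Cost:* no extra participants, but the effect-size part of the primary objective must be narrowed, and the future trial's effect assumption must come from other sources. The sample-size section already cites other trials for this.
- **(b) Several schools per arm.** State how schools are allocated and use an analysis that allows for school with the few degrees of freedom available (2 with two schools per arm, 4 with three). *Cost:* permissions in more of the 40 network schools, and possibly a norms survey in each added intervention school, because content is drawn from the school's own survey.
- **(c) Individual randomisation.** Delete the different-school phrase, run the blocks within school, include school in the model, and say how clustering by delivery group is handled. *Cost:* a risk of spillover within school, since the programme works through peers and norms. The planned request for discretion and the screening of controls may reduce or detect spillover but cannot rule it out. Using several schools would raise the survey cost in (b) here too.
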